# 2.5. Outcomes and Timing of Assessments.

# Table 6. Outcomes

Study Variable	Instrument	Outcome (Range)
Maternal: Measured at Baselin	e and 3*-, 6- and 12-months post-randomization	
Maternal Characteristics**	Trial Baseline Questionnaire 53,54	Self-reported age, education level, marital status, immigrant status and ethnicity, clinical history with depression or anxiety (severity, chronicity, number of prior episodes, and age at first episode, occupational status, number of children, pregnancy intention, pregnancy history, delivery and birth, sexual orientation.
Depressive Symptoms	Edinburgh Postnatal Depression Scale (EPDS)41	Mean continuous score of a 10-item scale (0-30)
Anxiety Symptoms	Generalized Anxiety Disorder Scale (GAD-7)42	Mean continuous score of a 7-item scale (0-21)
Response & Remission	Patient Health Questionnaire-9 (PHQ-9) 	Response: PHQ<10 Remission is defined as PHQ<5
Perceived Support	Multidimensional Scale of Perceived Social Support 	Mean continuous score of a 12-item scale (1-84)
Disability Assessment	World Health Organization Disability Assessment Schedule (WHODAS) 	Mean continuous score of a 12-item scale (0 – 48)
Quality of Life Assessment	EQ5D-5 Level (EQ5D-5L) 	Mean continuous score of a 5-item scale (1-25)
Trauma Symptoms	Abbreviated PTSD Checklist (PCL-6) 	Mean continuous score of a 6-item scale (1-30)
Patient-Reported Activation	Premium Abbreviated Activation Scale 	Mean continuous score of a 5-item scale (0-20)
Patient Satisfaction***	Client Satisfaction Questionnaire-8 (CSQ-8)61	Mean continuous score of an 8-item scale (1-32)
Therapeutic Alliance***	Working Alliance Inventory-Short Revise (WAI-SR)62	Mean continuous score of a 12-item scale (1-60)
Health Service Utilization	Health Service Utilization Form 	3, 6 months - Total score of a 16-item scale (0-32); 12 months – Total score of a 19-item scale (0 – 38)
Treatment Preference**	Delivery of treatment and treatment provider preference	Score of 0 or 1
COVID-19 Exposure	1-item question on COVID-19 exposure	Self-reported
Health Benefits Access and Use	2-item question on access and use of health benefits	Self-reported Self-reported
Sexual Orientation o	2-item question on sexual orientation	Self-reported
Home Visit Survey □	4-item question on home visit perspective	Self-reported
Intervention Costs	A survey of costs associated with the intervention	Self-reported and health records, related to the economic evaluation portion of the study
Treatment: Measured at every	session during treatment, unless otherwise indicated	
Dosage	Treatment Log 	Frequency of Sessions Attended
Therapy Quality****	Quality of Healthy Activity Program (Q-HAP)52	Mean continuous score of treatment-specific BA skills (0-4) and general counseling skills (0-4)
Session Depressive / Anxiety	Session-by-session EPDS  and GAD-7  scores	Mean continuous score of a 10-item scale (0-30) on EPDS and of a 7-item scale (0-21) on GAD-7
Homework Adherence	Treatment Log 	Mean continuous score of a 1-item question (0-2)
Adverse or Serious AEs	Anytime an Adverse Event (AE) or Serious AE occurs	Any event that represents a series threat to the safety of the mother or her child (see Appendix D)
Health Service Utilization	Health Service Utilization Form 	Total score of a 16-item scale (0-32)
List of Medications	List of Medications	Self-reported list of medications
COVID-19 Exposure	1-item question on COVID-19 exposure	Self-reported
Child: Measured at 6 to 24-more	nths post-child birth unless otherwise indicated	
Birth weight & Length	Retrieved from hospital chart or self-report†	Assessed at birth

Breastfeeding	Whether breastfeeding and if stopped age stopped.54	Total Number of Months (0-12)
Psychosocial Stimulation	Home Observation Measurement Evaluation 	Total score of a 45-item checklist
Mental Development	Bayley Mental Development Scales IV 	Mean continuous score of cognitive, receptive and expressive language development

\* Assessment period will be extended to account for post-treatment outcomes when there are perinatal-related interruptions to treatment (e.g., giving birth, obstetrical complications, COVID-19); \*\*Only at baseline; \*\*\*Measured at 3-months post-randomization only; \*\*\*\*Randomly selected for supervision, rated by self, peers, expert supervisor; †Self-report will be used when hospital charts are outside of the recruiting site; Measured at baseline for participants consented after addition of measure to baseline questionnaire, measured at 12-months post-randomization for those who completed baseline before addition of measure; Deasured once at 3-, 6- or 12-months post-randomization.

All measures proposed in the current study have been previously used and validated in one or more of the investigators' trials targeting perinatal mental health and selected because of their role in the presumed causal pathway. Our emphasis on mothers' self-reported data adheres to PCORI's methodology standards that emphasize that the patient population is the best source of information.

#### 2.6. Sample Size

The primary outcome measure will be participant's EPDS mean score at 3 months after randomization; the assessment period will be extended in the event that there is a hiatus to treatment due to significant perinatal-related life events (e.g., giving birth, obstetrical complications, COVID-19) or to one week after the last session if participants complete treatment after the 3 month-post randomization period. The study is designed to be a noninferiority trial with four arms: telemedicine specialist, telemedicine non-specialist, in-person specialist, in-person non-specialist. The two primary hypotheses are that telemedicine will be non-inferior to in-person, and that non-specialist delivery agents will be non-inferior to specialist delivery agents. The sample size calculation is based on an EPDS mean estimate of 7.93 (SD=4.68). Using a non-inferiority margin of 10% (i.e., EPDS score of 0.79) in relation to the mean), and an alpha=0.05 for our first comparison (NSP vs. SP) we require 431 participants in each of the two groups to provide greater than 80% power. To account for 10% drop out, the sample size is inflated to N=958 (479 per group, NSP vs. SP). Using a non-inferiority margin of 13% (i.e., EPDS score of 1.03 in relation to the mean), and an alpha=0.05 for our second comparison (TM vs. IP), we require an additional 268 IP participants. When combined with the 958 TM participants, this yields a total study sample size of N=1,226 which accounts for 10% loss to follow-up. Previous randomized non-inferiority trials have demonstrated that a 14% non-inferiority margin can be considered clinically meaningful.

We are planning a final sample size of N=1,230, four more participants than the power calculation requires. The reason for this n=4 over recruitment, is to provide flexibility due to the fact that we do not receive each site's recruitment numbers until the end of each day. These statistics have been reviewed and approved by our study statistician.

#### 2.7. Screening, Recruitment, and Consent

**2.7.1. Quantitative Data.** Across the three hubs, we anticipate assessing 18,280 participants for potential eligibility, obtaining informed consent to screen 9,140, and recruit and retain a sample size of N=1,230 women (see Figure 1). We anticipate that 50% of participants will be recruited in Toronto, and 25% each in Chapel Hill and Chicago, respectively. Participants will be recruited from all study sites though their networks of in-patient obstetrical units, family practice, obstetrical and mental health clinics, and community partners (see Recruitment Poster – 4 Arm Without Tabs, Appendix E – Study Documents, pg 123). Referrals will also be elicited from clinicians from site hospitals and satellite clinics who will send patient contact information to the research coordinator. Relevant stakeholder groups, such as Life with a Baby, will also be provided with information about the trial to share with their members. Interested individuals can contact the trial for more information.

To help alleviate the mental health burden that COVID-19 imposes on our health care systems, physicians not affiliated with a study site will be able to refer their patients to the SUMMIT Protocol V20: 25 Oct 2024

SUMMIT Trial for screening and enrollment, if eligible and willing. This includes referrals from physicians not affiliated with the trial (external referrals) and referrals between recruitment sites (internal referrals). Internal referrals will occur among patients who express interest in participating in the trial at a study site where recruitment is on temporary hold due to treatment provider capacity.

[figure not shown]
- 1. **External referrals:** Study Investigators will notify their physician colleagues not affiliated with a study site that the SUMMIT Trial is open to their patients (*see Email for External Physicians, Appendix E Study Documents, pg 126 and 129*) and provide a description of the study (*Information for External Physicians, Appendix E Study Documents, pg 125 and 128*). Physicians will briefly describe the study to their patients, and ask them if they are interested in learning more. If the patient is interested, the physician will then request their patients' permission to send their name and contact information to the study team. Potential participants may also learn of the trial through relevant stakeholder groups in which they are members (for example, Life with a Baby). Interested individuals will be able to contact the trial for more information.
- 2. Internal referrals: Patients who express interest in participating in the trial at a study site may not be able to immediately access treatment if randomization is temporarily paused due to reaching treatment provider capacity. In this event, patients will be given the option of a referral to the trial at a different site that is still able to accept new participants. If they agree, the study team at the referring site will request the patient's permission to send their contact information to the study team at the second site. Contact information will be faxed or encrypted and sent via secure hospital email to a secure hospital email at the second site. No identifying information will be included in the title or body of the email. Participation in the trial at the second site will not affect the patient's care at the referring site. Upon receipt of the contact information, the study team at the second site will contact the patient and follow the consent procedures described in this protocol.

Women will be contacted either by a trained research assistant, a treating physician or another member of the circle of care to ask whether they can be contacted by one of the trained research assistants. They will then receive a brief overview of the study by a research assistant, while an in-patient, visiting an out-patient clinic, or over the phone. Women who agree will then be fully informed of the study procedures by the research assistant, and given an informed consent form (see Informed Consent Form, Appendix E − Study Documents, pg 4 and 16) to review. Women will be given as much time as they need to decide whether they wish to participate, and the research assistant will answer all questions they may have. Once they sign the consent form, women will be screened using the Edinburgh Postnatal Scale for Depression (EPDS≥10^41) and General Anxiety Disorder (GAD)-7 for eligibility. If an EPDS administered in the last 7 days is in the patient's clinical chart, we will use and enter that score for screening instead of asking the patient to complete the scale again. In the interest of patient-centered care, women who give their permission may also complete informed consent

over the phone, witnessed by a third-party. These women will be mailed a consent form and be fully informed of the study procedures by the research assistant over the phone. If they decide that they want to participate, they will give verbal consent verified by a third-party (a second study team member), and will then be emailed links to screening measures. These women will be provided with a self-addressed, stamped envelope to mail their signed consent forms back to the site, and will then be sent a consent form with their own signature and the name and signature of the RA who obtained their informed consent for their files.

To reflect the pragmatic and patient-centered nature of the trial and in an effort to uphold recommended social distancing guidelines for both participants and research staff, we will not ask participants to mail back signed consent forms during COVID-19 and will instead rely on verbal consent given over the phone and confirmed by a third party. To ensure a paper trail, participants will also indicate their consent in REDCapTM. During verbal consent, participants will be sent a link to a consent form in REDCapTM. The consent form will be the same as the form they receive for verbal consent, but will include checkboxes for each permission and a checkbox to indicate that they agree to participate in the trial. The research assistant obtaining informed consent and the third party will add their names and signatures to the form to indicate that they explained the study and confirmed consent. Participants will not enter their names in REDCapTM during this process. Consent forms will only be identified by participant ID and will be linked to participant profiles in REDCapTM, respectively.

At the American sites, research assistants will either be bilingual or use a translation service so that they can explain the study to potential participants who only speak Spanish and a consent form will be provided in that language. All study questionnaires and the BA intervention will be conducted in Spanish for Spanish-speaking participants. Recruitment rates will be closely monitored. Self-referrals will also be accepted if recruitment rates are low. Brochures outlining the study's aims, potential impact and inclusion/exclusion criteria will be provided to all recruitment sites (see Brochure, Appendix E – Study Documents, pg 115 and 117). Trained research assistants will follow-up with each appropriate referral and obtain informed consent (Figure 3). Recruitment will begin in January 2020 and continue until March 2023 (39 months in total) at all sites.

**Figure 4: Recruitment Process** 

- **2.7.2. Qualitative Interviews.** A team of trained interviewers will collect qualitative data through semi-structured, in-depth interviews and focus group discussions. These individuals will be independent from both the recruitment and data teams. Topic guides were developed and reviewed with a range of key stakeholders to ensure questions are relevant and acceptable.
- **2.7.2.1.** Qualitative Phase 1 (Sep 2019 to Apr 2020). All NSPs, specialist providers, and supervisors will take part in qualitative semi-structured interviews to explore their work experience related to training and supervision. All potential treatment providers will be informed that they will be required to complete interviews when they are recruited. All successful applicants who accept the positions as providers or supervisors will understand that in accepting the position, they will participate in semi-structured interviews that will be used in the research study as a part of their job.
- **2.7.2.2.** Qualitative Phase 2 (May 2020 to Mar 2024). A subset of study participants, significant others, treatment providers and supervisors, and a wide range of stakeholders (patient advocates, health professionals, and policy makers) will be invited to participate in qualitative, semi-structured interviews to examine key aspects of the intervention, including content, delivery and modality, enactment of key messages, scalability, and, where applicable, supervision procedures. In the first six months of this process, we will also ask several semi-structured questions to examine whether aspects of the treatment content or delivery were modified in light of COVID-19.

**Participants.** – We will conduct the qualitative interviews with representative subsets of perinatal participants (n=300) across the four arms, selected to represent different variables such as symptom severity, perinatal period (antenatal and postnatal), sociodemographic

variables, and treatment completion status (completers and non-completers). Potential participants will be identified by the Data Manager and approached by a research assistant if they would consider taking part in the interviews. A research assistant will approach those willing to explain the interview process and secure informed consent (see Informed Consent Form – Participant Qualitative, Appendix E – Study Documents, pg 37). The research assistant will answer any questions and the women will be given as much time as they need to make an informed decision. Please note that this research assistant is independent and has not conducted any baseline or follow-up assessments with potential participants.

**Significant Others.** – Up to 60 significant others will be interviewed as a part of Qualitative Phase 2. Participants will indicate in their informed consent form if their partners can be contacted to participate in interviews about their experiences related to the treatment intervention. If they indicate yes, we will ask the participants to speak with their significant others and let their significant other know that they may be contacted by a research assistant. Spouses or partners are preferred but we will accept any significant other that the participant identifies. If the participant agrees, a research assistant will contact their partner and explain the interview process and secure informed consent (*see Informed Consent Form – Partners Qualitative, Appendix E – Study Documents,* pg 46) to review. The research assistant will answer any questions the partners may have via whatever means of communication they prefer (e.g., phone or email), and the partners will be given as much time as they need to make an informed decision.

**Treatment Providers and Clinical Leads.** – All NSPs, specialist providers and clinical leads will be expected to participate in the Qualitative Phase 2 interviews as a part of their job description. Treatment providers and clinical leads were previously asked to provide informed consent to participate in up to three interviews and then will be given a consent addendum form to agree to participate in an additional five interviews for a total of eight interviews.

Other Stakeholders. – Other stakeholders include relevant health professionals (e.g., nurses, midwives and physicians from mental health, obstetrics and family medicine), patients and patient advocates, telemedicine and insurance experts, study staff, and policy makers identified by the PIs at each site and invited to engage in the trial as committee members and consultants. Stakeholders are informed that qualitative interviews about their views and experiences are a voluntary part of the study and that they will be sent invitations to participate. The research assistant will send a link to the informed consent in REDCapTM by email (see Informed Consent Form – Stakeholders Qualitative, Appendix E – Study Documents, pg 55, Informed Consent Form – Staff Qualitative, Appendix E – Study Documents, pg 62 ,SUMMIT Stakeholder Email Interview Invite – Appendix E – Study Documents, pg 61 and SUMMIT Staff Email Interview Invite – Appendix E – Study Documents, pg 68). The stakeholders will be able to ask the research assistant any questions they may have by phone or email, and the stakeholder will be given as much time as they need to make an informed decision. The RA will follow up with stakeholders who do not respond to the email to check if they have any questions and if they are interested in participating.

#### 2.8. Randomization

All participants will be stratified by perinatal period (antenatal vs. postnatal) and then randomized within site to one of the four arms, unless restricted to two arms due to COVID-related institutional restrictions of in-person care (see section 2.2.3.2) and using a web-based randomization service as part of REDCap™. Randomization will occur only after informed consent has been obtained and all baseline measures have been completed and all inclusion/exclusion criteria verified with the participant. We will enroll equal numbers in each of the four intervention arms. This strategy allows sufficient power to determine whether NSPs are no less efficacious than specialists and telemedicine is no less efficacious than in-person treatment, respectively, in settings that collectively assure ethnic and racial diversity, as well as potential heterogeneity in age, variability in symptom severity as well as access to resources.

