1.5. Randomization

All SUMMIT participants are stratified by perinatal period (antenatal vs. postnatal) and were initially (Phase 1) randomized within site to one of four arms (see [Figure 2](#)). However, during the early part of the COVID-19 pandemic (Phase 2) when in-person care was prohibited, participants were randomized to only one of two arms: TM NSP and TM SP ([Figure 2](#)). All sites resumed randomization to all 4 arms 16 months later (Phase 3). Given that Phase 2 consisted of

Figure 2. Randomization strategy

*Randomization can shift to the two telemedicine arms based on site specific, COVID-related institutional restrictions, and once enrollment to in-person arms is complete.

randomizing participants exclusively to TM, there was an imbalance in participant assignment between the IP and TM arms. To address this, a weighted randomization approach (3:1, favoring IP) was used in Phase 3 in which a reduced percentage of

participants were randomized to the TM arms to ensure that the study's sample size targets will be met, and the final sample has an equal number of IP and TM participants. Due to the Omicron wave in December 2021 and January 2022, participants were randomized to TM-only again and randomization switched back to a 1:1 ratio. However, sites were permitted to switch between a 1:1 TM-only (2 arm) and a 1:1:1:1 both TM and IP (4 arm) randomization scheme based on site-specific COVID restrictions and Infection Prevention and Control (IPAC) recommendations. Sites began resuming Phase 1 randomization to IP in the 1:1:1:1 ratio in January 2022, and all sites returned to Phase 1 randomization by April 2022. Randomization to all 4 arms will be followed until in-person arms are fully enrolled after which randomization 1:1 to the two telemedicine arms will be followed.

Table 2: SUMMIT Outcomes (A more detailed list can be found in [Appendix 1](#)).

Study Variable	Instrument	Outcome (Range)
Maternal: Measured at Baseline and 3*-, 6*- and 12*-months post-randomization		
Maternal Characteristics**	Trial Baseline Questionnaire ^{6,7}	Self-reported age, education level, gender identity and sexual orientation, marital status, immigrant status and ethnicity, clinical history with depression or anxiety (severity, chronicity, number of prior episodes, and age at first episode), occupational status, number of children, pregnancy intention, pregnancy history, delivery and birth.

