1.6.2. Primary Aim 2 (Telemedicine vs. In-Person) Comparison

The primary outcome measure is an EPDS mean score at 3 months post-randomization. The sample size calculation is based on an EPDS mean estimate of 7.93 (SD=4.68)³⁰. Using a non-inferiority margin of 13% (i.e., EPDS score of 1.03 in relation to the mean), and an alpha=0.05, we require an additional 268 IP participants ([Table 4](#)).

Table 4: Non-inferiority margin in relation to sample size for Phase 3 comparisons

Non-inferiority margin	Power	Sample size per primary question	Total sample size + 10% dropout*	Total sample size + 20% dropout
10%	80%	431	958	1078
13%	80%	241	536 (268 per group)	604
14%	80%	221	492 (246 per group)	556

*Current dropout rates are <10% at primary outcome of 3-months post-randomization

When combined with the 958 TM participants, this yields a total study sample size of N=1,226 which accounts for 10% loss to follow-up ([Table 5](#)).

Table 5: Primary aims and required sample sizes

Primary Aim [¥]	Non-inferiority Margin	Power	Required sample size + 10% drop out
SP vs. NSP [¥]	10%	88%	958 telemedicine
IP vs. Telemedicine	13%	80%	268 in-person*
	Total		N=1226*

[¥]We acknowledge that the in-person sample is contained in the first hypothesis. This will result in the SP vs NSP comparison having up to 88% power. *We will over-recruit to account for protocol deviations where participants were switched from in-person to telemedicine due to the COVID-19 pandemic.

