Aim 2 is to show that TM is non-inferior to in-person (N=268 per group, IP vs TM, [Table 4](#)).

Aim 1 and Aim 2 will initially be analyzed using a non-inferiority t-test (under the assumption that randomization will serve to balance out potential confounders). Each t-test will look at the confidence interval around the difference in EPDS scores (say between TM and IP) and see if the upper bound contains the non-inferiority margin (upper bound for the case in which we take the difference to be TM minus IP). In addition, we will run a linear regression model with mode, agent, and a mode by agent interaction term to assess whether an interaction between mode and agent exists. In the unlikely event that randomization was not able to reduce bias by balancing out confounders, we will adjust for variables found to be imbalanced at baseline.

Rules on the number of variables allowed in a multivariable model will be followed. The rule on number of variables in a **linear** regression is to take the total number of observations divided by 10. Given our trial sample size, we do not have any concerns with overfitting our linear model for our **covariates of interest** (education level, marital status, ethnicity, baseline severity and chronicity, timing of treatment, compliance, perceived support, and medication). For the **logistic** regression analyses, the number of predictors will be based on the smaller of the two outcome categories divided by 10^{36} .

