3.4.1.1. COVID-related Adjustments (Phase Analysis)

In order to determine whether the participants recruited in Phase 2 can be combined with those in Phase 3 in the larger trial, we will examine a potential interaction between group (SP, NSP) and phase (2 and 3) in relation to change in EPDS and GAD scores. To examine this, a linear mixed model will be run for the outcome EPDS and another for the outcome GAD. Each model will contain a group (SP, NSP), Phase (2 and 3), and a group by phase interaction term. A comparison of Phase 1 (pre COVID phase) to Phase 3 (return to IP phase) will not be carried out as the sample size in the first phase (n=23) is too small to detect statistical differences; however, we will conduct a sensitivity analysis on our primary outcome (EPDS scores at 3-month post-randomization) which includes this portion of the sample.

The study analyses will be carried out as originally planned on the entire sample of participants across all 3 phases. Should we find a group by phase interaction, we will also run separate analyses by phase (2 and 3) and compare their results to the model on the entire sample.

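### The telemedicine versus in-person comparison (Aim 2) is described with three different group sizes, and its stated 80% power is an equal-group figure that neither reproduces nor fits the planned 958 versus 268.

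*Protocol*

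**What the plan says.** The current text describes the Aim 2 groups in several ways.

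- **Four equal arms.** Protocol 2.8: "We will enroll equal numbers in each of the four intervention arms". The next sentence says this strategy gives sufficient power for both primary questions.
- **Equal modes.** SAP 1.5, explaining the 3:1 weighting used in Phase 3, gives as part of its purpose that "the final sample has an equal number of IP and TM participants". The same section later states the rule now in force: "Randomization to all 4 arms will be followed until in-person arms are fully enrolled", and then only the two TM arms stay open.
- **268 per group.** SAP 3.4.1: "Aim 2 is to show that TM is non-inferior to in-person (N=268 per group, IP vs TM", with a pointer to Table 4.
- **958 and 268.** SAP 1.6.2: "When combined with the 958 TM participants, this yields a total study sample size of N=1,226". Protocol 2.6 has the same construction: "When combined with the 958 TM participants, this yields a total study sample size of N=1,226 which accounts for 10% loss to follow-up".

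On who is analysed, SAP 3.4.1 includes an intent-to-treat analysis by randomized group, and SAP 3.4.1.1 says "The study analyses will be carried out as originally planned on the entire sample of participants across all 3 phases".

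On power, the 13% row of Table 4 gives 241 per group (268 after 10% dropout) for 80%. Table 5 repeats 80% for Aim 2 beside the 268 in-person participants. For Aim 1 the same table raises power to 88%, and its footnote explains that the in-person sample is counted too.

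**The concern.** Four equal arms out of 1,226 would be about 307 each, or 613 per mode. That cannot stand beside 268 in-person participants, and 268 per group is not the same comparison as 958 versus 268. Depending on which sentence is followed, power at the 13% margin runs from about 68% to about 98%, while the SAP reports one figure, 80%. Table 5 updates Aim 1 to the full sample but leaves Aim 2 at the equal-group figure. The 13% row also sets the in-person target, and so N=1,226, which makes an arithmetic slip there visible in the headline sample size. At stake are the accuracy of the power and sample-size figures for one of the two primary comparisons, and a clear statement of which groups are compared.

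**Working it through.** **Inputs**
- Mean and SD, SAP 1.6.2: "The sample size calculation is based on an EPDS mean estimate of 7.93 (SD=4.68").
- Margins: 10% = 0.793 (Table 3); 13% = 0.13 × 7.93 = 1.031; 14% = 0.14 × 7.93 = 1.110.
- True difference 0. Table 3 states this for Aim 1; I assume it for Aim 2.
- Alpha 0.05. Aim 1 reproduces only if this is one-sided.
- Decision rule, SAP 3.4.1: upper bound of the 95% confidence interval against the margin. I read the interval as two-sided, which is one-sided 0.025.
- Loss to follow-up 10%.

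**Formulas**
- n per group = 2 × (SD/margin)² × (z₁₋α + z₀.₈)², with z₀.₈ = 0.842
- Power = Φ(margin / (SD × √(1/n₁ + 1/n₂)) − z₁₋α)
- z₁₋α = 1.645 at one-sided 0.05 and 1.960 at one-sided 0.025

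A noncentral t calculation agrees to within 0.2 percentage points.

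**Step 1. The plan's figures that reproduce (one-sided 0.05)**
- 10% row: 2 × (4.68/0.793)² × 2.487² gives 431, as stated. 431/0.9 gives 479 per group, 958 in all.
- 14% row: 220, against 221 stated.
- Aim 1 on the full sample: 613 × 0.9 = 551.7 per group gives 87.9%, matching the 88% in Table 5.

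The method is therefore recovered.

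**Step 2. The 13% row**
- 2 × (4.68/1.031)² × 2.487² = 254.8, so 255 per group. 255/0.9 gives 284. The table has 241 and 268.
- The inflation step is right (241/0.9 = 268); the 241 is not.
- A size of 241 corresponds to a margin of about 1.06, or 13.4% of 7.93.
- At one-sided 0.025 the requirement is 324 per group.

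**Step 3. Power for each description at the 13% margin**

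For 241 versus 241: SE = 4.68 × √(2/241) = 0.426 and 1.031/0.426 = 2.418. Then Φ(2.418 − 1.645) = 78.0% and Φ(2.418 − 1.960) = 67.7%.

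For 862 versus 241 (958 × 0.9 and 268 × 0.9): SE = 4.68 × √(1/862 + 1/241) = 0.341 and 1.031/0.341 = 3.023. Then Φ(1.378) = 91.6% and Φ(1.063) = 85.6%.

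| Description | Evaluable TM / IP | One-sided 0.05 | Two-sided 95% CI rule |
|---|---|---|---|
| 268 per group (SAP 3.4.1) | 241 / 241 | 78% | 68% |
| 958 and 268 (Protocol 2.6, SAP 1.6.2) | 862 / 241 | 92% | 86% |
| Equal modes out of 1,226 (Protocol 2.8) | 552 / 552 | 98% | 96% |

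No row gives 80%.

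**Step 4. Is 268 in-person enough for the planned split?** With 862 evaluable TM participants, 80% power needs 150 evaluable IP participants at one-sided 0.05 (167 with loss), or 200 under the 95% interval rule (223 with loss). The planned 268 exceeds both. At 20% loss, the split still gives 89% and 81%.

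**The case against.** The best defence is that the documents, read together, do indicate the Aim 2 analysis. SAP 3.4.1.1 analyses the entire sample, SAP 3.4.1 includes intent-to-treat, and SAP 1.6.2 adds the in-person participants to the 958 TM. The 268 per group in SAP 3.4.1 can be read as a pointer to a required minimum. Aim 1 is written the same way, with 479 per group, although the Table 5 footnote says Aim 1 contains the in-person sample as well. This stands. A reader might infer that nothing determines which TM participants enter the test, or that 268 of 958 would be picked later. No passage plans such a selection, and those cited point to all of them.

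The equal-numbers phrase in SAP 1.5 is attached to the Phase 3 weighting, described in the past tense, and the section then gives a rule that leads to unequal groups. It is leftover wording more than a live plan. Protocol 2.8 does allow for two-arm periods, but its equal-numbers sentence has no such qualification and carries the power claim.

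A reader might also infer that the larger TM group removes the reason for widening the margin from 10% to 13%. It does not. With 862 versus 241 at the 10% margin, power is Φ(0.793/0.341 − 1.645) = 75%, or 64% under the 95% interval rule. The margin at which 80% is reached is 0.848 (10.7%) or 0.955 (12.0%), above 10% either way. The recruitment reason in SAP 1.6.2.1 is not contradicted by these figures.

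What the defence does not remove is the unqualified sentence in Protocol 2.8, the 268 per group where SAP 3.4.1 specifies Aim 2, the 13% row, and the 80% in Table 5.

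**Conclusion.** The point holds as a should-fix correction of stated figures. The Aim 2 group sizes are inconsistent in current text. The 13% row of Table 4 is too low by 14 per group (255 against 241; 284 against 268 with loss). The 80% in Table 5 belongs to an equal-group comparison that the trial does not plan, and even there the figure is about 78%, or 68% under the two-sided 95% interval rule.

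It would be tempting to conclude that Aim 2 is underpowered; the documents do not support that. For 958 versus 268, power is about 92% or 86%, so the stated 80% errs on the cautious side. Power falls below 80% only if Aim 2 is really run with 268 per group, which the entire-sample statement contradicts.

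These figures assume SD 4.68 in both groups, a true difference of zero, 10% loss, a two-sided 95% interval, and all randomized TM and IP participants analysed together. A comparison limited to participants randomized while in-person arms were open would have less power; the documents do not give the counts to calculate it.

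**What to change.** 1. Protocol 2.8: remove the equal-numbers sentence or replace it with the planned 958 TM and 268 IP, and tie the power claim to that split.
2. SAP 1.5: mark the equal-numbers phrase as the past aim of the Phase 3 weighting.
3. SAP 3.4.1: in place of 268 per group, state that the Aim 2 test uses all randomized TM and IP participants (958 versus 268 planned).
4. SAP Table 4, 13% row: at one-sided 0.05, change to 255 per group, 568 in total with 10% loss (2 × 284) and 638 with 20% loss (255/0.8 = 319 per group). If the table is moved to the 95% interval rule, the entries are 324 per group, 720 in total (324/0.9 = 360 per group) and 810 (324/0.8 = 405 per group), and the other rows must be recalculated on the same basis.
5. SAP Table 5: restate Aim 2 power for 958 versus 268 at the alpha of the decision rule, about 86% for a two-sided 95% interval (about 92% at one-sided 0.05), and say which is meant.

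The cost is text and table edits in both documents. The in-person target of 268 can stand, because the planned split exceeds 80% power under either alpha.
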